### **8.6.4. Drug Storage and Drug Accountability**

Unless notified otherwise by the Sponsor, all supplied Xeris' investigational product is to be stored at controlled room temperature between 20°C to 25°C (68° to 77°F), and drug solution should be clear and of a water-like consistency at time of use.

The investigator or an approved study staff will ensure that the study medications are stored in a secure area under recommended storage conditions and in accordance with applicable regulatory requirements.

The site will maintain appropriate documentation of continuous storage conditions and these records will be monitored in an on-going basis by the monitor. Any deviations in the storage conditions must be documented (including minimum and maximum temperature excursion as well as estimate of total duration of storage outside the recommended storage conditions). Such deviations must be communicated to the Sponsor as soon as identified by the site with appropriate course of action taken regarding the future use of the study medications upon consultation with Xeris Pharmaceuticals.

The investigator must maintain adequate records documenting the receipt, use, loss or other disposition of the investigational drug products and supplies. Used and unused investigational product will be returned to Xeris. Other used supplies will be destroyed according to local regulation and site level SOPs following accountability by Xeris Pharmaceuticals or its designee.

### **8.7. CGM Devices**

Sites will be supplied with sufficient iPRO2 recorder devices to have a dedicated device for each subject. The sites will store this device between the CGM data gathering periods and will clean the devices before return to Xeris at the end of the study.

The sites will be supplied sufficient sensors for the study.

Subjects using their own CGM may continue to use their own device during the study, but these will not be re-supplied through the study.

### **8.8. Glucose Meters for Self-Monitoring and Calibration of the CGM Devices**

Subjects will be supplied Contour Next meters and strips for use during the CGM data collection periods of the study. Subjects must use the supplied meter during these periods of the study, and may use it at other times during the study, but are not required to do so.

### **8.9. Subject Data Log and Smartphone**

The study will capture diabetes management data using the iPRO2mylog application on their own device. The application is available in Apples' and Google's respective online stores. Xeris will make smartphones available for subjects, during the course of the study, if they do not own a compatible smartphone.

### **8.10. Concomitant Medications**

Subjects should be on a stable dose of all concomitant medications for at least 30 days prior to Screening. All subjects must have their concomitant medications reviewed at each visit. Medications taken within 4 weeks before Day 1 will be documented in the CRF. Any changes to a subject's concomitant medication regimen will be documented. Investigators are encouraged to avoid adding to or changing a participant's medications until week 4 of study participation unless deemed medically necessary.

There are not medications that are specifically prohibited during participation in this study, except the medications (e.g., anticoagulants) listed under the exclusion criteria (see Section 8).

## **9. STUDY PROCEDURES**

### **9.1. Outpatient Insulin Dose Adjustment During Run-in and Treatment Phases Weeks -1-4**

Subjects' insulin doses should be reviewed and adjusted to maintain current ADA recommended glycemic targets of pre-prandial PG of 80-130 mg/dL and post-prandial PG<180 mg/dL, per investigator's discretion.

### **9.2. CGM, Glucose Meter, Electronic Diary and Pump Data**

CGM, glucose meter, electronic diary data, and insulin pump data for CSII users should be collected weekly. The subject is expected to return to the clinic for data upload. The Medtronic iPRO2 platform will be familiarized with both the investigator and the subject.

### **9.3. Euglycemia Maintenance Procedure**

The subject will begin fasting at midnight. The subject must have been fasting for a minimum of eight hours before the induction procedure may begin.

Upon the subject's early morning arrival to clinic\*, their plasma glucose should be maintained within a target range between 80-120 mg/dL, via IV insulin infusion and/or IV glucose infusion. This target range should be obtained as soon as possible. The plasma glucose should be remeasured every 30 minutes and appropriately treated until it reaches the desired target range has been reached. Afterwards, the plasma glucose may be rechecked every hour.

\*Per institutional/departmental policy and the approval of the sponsor a subject may be brought in the evening prior to the induction procedure.

**Table 3: Recommended Guidelines for Insulin Infusion Rate Management Following Measured PG**

Below Goal Range Less than 90 mg/dL	Within Goal Range 90-120 mg/dL	Above Goal Range Over 120 mg/dL

Less than 70 mg/dL
 
 
• Turn off infusion
 
• Follow Hypoglycemia orders***
 
• Recheck BG and re-treat every 15. Then proceed according to the appropriate column of this table for next measured BG.
 
 
70 – 80 mg/dL
 
 
• Turn off infusion.
 
• Check BG in 30 minutes.
 
• Once BG is > 80mg/dl resume insulin infusion after moving one column to the left
 
 
80-90 mg/dL
 
If BG decreased by 30 mg/dL or more, or previous BG 80-90 mg/dL
 
 
• Move left one algorithm and adjust rate per BG.
 
• If already at ½ Standard move, left to ¼ Standard Algorithm and adjust rate per BG.
 
• If already at ¼ algorithm, may remain there.
 
 
If BG decreased less than 30 mg/dL and/or previous BG was in goal range
 
 
• Adjust rate in current algorithm per BG.
 
	
If BG decreased by >30 mg/dL between checks
 
 
• Move left one algorithm and adjust rate per BG.
 
• If already at ½ Standard, move left to ¼ Standard (Low) Algorithm and adjust rate per BG
 
 
If BG DECREASED by 1-30mg/dl or INCREASED by any amount
 
 
• Adjust rate in current algorithm per BG
 
	
IF BG decreased by more than 50 mg/dL
 
 
• Move left one algorithm and adjust rate per BG.
 
• If already at ½ Standard, move, left to ¼ Standard (Low) Algorithm and adjust rate per BG.
 
• Check BG in 15 minutes if decrease was over 100 mg/dL.
 
 
If BG decreased by 25 – 50 mg/dL
 
 
• Adjust rate in current algorithm per BG
 
 
If BG increased by any amount, remained the same or decreased by less than 25 mg/dL
 
Step 1. Remain in current algorithm and adjust rate per BG.
 
Step 2. If after remaining in current algorithm and next BG check continues to increase by any amount or decrease by less than 25 mg/dL, move right one algorithm
 
Step 3. Check BG at next time point per protocol, and restart at step 1 if appropriate.


**Table 4: Recommended Euglycemia Maintenance IV Insulin Infusion Rate Algorithms**

BG mg/dL	# 1/8 units/hr (ml/hr)*	# 1/4 units/hr (ml/hr)*	# 1/2 units/hr (ml/hr)*	# 1 Standard units/hr (ml/hr)*	# 2 units/hr (ml/hr)*	# 3 units/hr (ml/hr)*	# 4 units/hr (ml/hr)*	# 5 units/hr (ml/hr)*	# 6 units/hr (ml/hr)*
80-90	0.1 (0.5)*	0.2 (1)	0.3 (1.5)	0.5 (2.5)	0.6 (3)	0.8 (4)	1.0 (5)	1.2 (6)	1.4 (7)
90 - 120	0.2 (1)	0.3 (1.5)	0.5 (2.5)	0.7 (3.5)	0.8 (4)	1.0 (5)	1.2 (6)	1.4 (7)	1.6 (8)
121-160	0.3 (1.5)	0.4 (2)	0.7 (3.5)	0.9 (4.5)	1.1 (5.5)	1.2 (6)	1.4 (7)	1.6 (8)	1.8 (9)
161-180	0.4 (2)	0.5 (2.5)	1 (5)	1.1 (5.5)	1.3 (6.5)	1.5 (7.5)	1.7 (8.5)	1.9 (9.5)	2.1 10.5
181-220	0.5 (2.5)	0.6 (3)	1.2 (6)	1.3 (6.5)	1.5 (7.5)	1.7 (8.5)	1.9 (9.5)	2.1 (10.5)	2.3 11.5
221-260	0.6 (3)	0.8 (4)	1.5 (7.5)	1.7 (8.5)	1.9 (9.5)	2.1 (10.5)	2.3 (11.5)	2.5 (12.5)	2.7 (13.5)
261-300	0.8 (4)	1 (5)	2 (10)	2.2 (11)	2.4 (12)	2.6 (13)	2.8 (14)	3.0 (15)	3.2 (16)
Over 300	1 (5)	1.3 (6.5)	2.5 (12.5)	2.8 (14)	3.0 (15)	3.2 (16)	3.4 (17)	3.6 (18)	4.0 (20)

\*When using 100 units of regular insulin per 500ml of saline, the pump infusion rates in parentheses apply.

#### 9.4. Hypoglycemia Induction Procedure

After the data are checked and PG confirmed to have been within range the visit proceeds. If the PG is < 70 mg/dL or > 200 mg/dL, the subject must be rescheduled.

The hypoglycemia induction procedures have to be initiated in the morning defined as 6 A.M. to 12 P.M. Subjects should have both arms cannulated one for infusion and one for sampling. Separate infusion pumps for insulin and glucose should be ready to begin the procedure. Subjects should remain blinded to their PG levels throughout this procedure.

The venous sampling arm should be kept warm in a heated hand box throughout the treatment procedure, in order to achieve “arterialized” samples. The subject’s hand should be monitored at least twice an hour to assure it remains warm during the hypoglycemia induction procedure, and if it turns cool appropriate measures take to keep it warm.

The periods of the procedure and what is adjusted are outlined in Table 5.

**Table 5: Hypoglycemia Induction Overview**

Period Reference	Measured PG (mg/dl)			Minimum Time	Insulin infusion		Glucose infusion
	Target	+/-	Range		Insulin infusion rate	Adjustments	Glucose infusion rate
Overnight stabilization	100	20	80-120		Euglycemia algorithm	Yes	0, but ready
Baseline stabilization	100	10	90-110	60 min.	20 mU/(BSA*min)	Change only if insufficient	As needed for stabilization
Start induction 1st step	70				20 mU/(BSA*min)	Change only if insufficient	Decrease to drop PG at a rate of $\approx 1$ mg/(dl*min)
Induction 1st step	70				20 mU/(BSA*min)	Change only if insufficient	Increase when PG nears target
70 mg/dl stabilization	70	5	65-75	30 min.	20 mU/(BSA*min)	Change only if insufficient	As needed for stabilization
Start induction 2nd step	70				20 mU/(BSA*min)	Change only if insufficient	Decrease to drop PG at a rate of $\approx 1$ mg/(dl*min)
Induction 2st step	50				20 mU/(BSA*min)	Change only if insufficient	Increase when PG nears target
50 mg/dl stabilization	50	5	45-55	30 min.	20 mU/(BSA*min)	Change only if insufficient	As needed for stabilization
Normalization	100		80-140		0	No	As needed until PG > 70 mg/dl

#### 9.4.1. Baseline Stabilization with Constant Insulin Infusion Rate

- After the baseline procedures are complete the insulin infusion rate is set at 20 mU/(BSA\*min). The rate should be kept constant until the hypoglycemia procedure is over unless it proves insufficient. The BSA is calculated using the formula  $BSA = 0.007184 * W^{0.425} * H^{0.725}$  where 'W' is weight measured in kg and 'H' is height measured in cm [Du Bois].
- Based on PG measurement every 5 minutes the glucose infusion rate (GIR) is adjusted to maintain plasma glucose within in the 90-110 mg/dL range with a target of 100 mg/dL.
- Time 0 begins at the first PG reading within the range of 90-110 mg/dL.
- The PG will be measured every 5 minutes for sixty minutes:
  - If > 2 of 12 PG measurements are not within the specified range, the sixty minute stabilization period will restart.
    - This baseline stabilization must be completed within 120 minutes.
  - If no more than 2 of 12 PG readings are outside the range, subject will continue to step Hypoglycemia induction, 1st step.
  - Plasma Glucose and assessment of hypoglycemia symptoms will be measured as a baseline
  - Hypoglycemia symptoms will be assessed every ten minutes while subject is above 70 mg/dL
  - Two sets of baseline counter regulatory hormone blood samples are drawn 10 minutes apart once the sixty minutes are met (e.g. 60 and 70 minutes)

#### 9.4.2. Hypoglycemia Induction, 1st Step

- The GIR will be decreased with the goal of achieving a PG change rate of  $-1$  mg/(dL\*min) to achieve the target of 70 mg/dL.
- At every PG measurement the estimated time to the 70 mg/dL target will be assessed and the GIR adjusted accordingly.
  - Hypoglycemia symptoms will be assessed every five minutes when subject is below 70 mg/dL

**9.4.3. 70 mg/dL Stabilization**

1. The GIR will be adjusted to maintain the target  $70 \text{ mg/dL} \pm 5 \text{ mg/dl}$  guided by PG measurements every 5 minutes.
2. Should PG briefly be lower than target range, the steps may be prolonged.
3. When the plasma glucose has been maintained at  $70 \text{ mg/dL} \pm 5 \text{ mg/dl}$ , for a minimum of 30 minutes and the described data collection procedures completed. Then the next phase may begin.

**9.4.4. Hypoglycemia Induction and Stabilization, 2nd Step**

1. The GIR will be decreased with the goal of achieving a PG change rate of  $-1 \text{ mg/(dl*min)}$  to achieve the target of  $50 \text{ mg/dL}$  but no greater than  $54 \text{ mg/dL}$ .
2. The PG will be measured every 5 minutes for thirty minutes:
  - a. If 1 PG measurement is greater than  $54 \text{ mg/dL}$  during the thirty minutes; the 2nd step will re-start, per investigator discretion.
3. At every PG measurement the estimated time to the  $50 \text{ mg/dL}$  target will be assessed and the GIR adjusted accordingly.
  - a. Plasma Glucose and assessment of hypoglycemia symptoms will be measured and assessed every 5 minutes.
4. When the plasma glucose at  $50 \text{ mg/dL}$  has been maintained for a minimum of 30 continuous minutes, two sets of blood samples for assessment of counter regulatory hormones will be drawn 10 minutes apart (e.g. 30 and 40 minutes).

#### 9.4.5. Normalization to Euglycemia

1. When the plasma glucose at 50 mg/dL has been maintained for a minimum of 30 minutes and the described data collection procedures completed, the IV insulin infusion will be stopped and the IV glucose infusion will continue.
  - a. Plasma Glucose and assessment of hypoglycemia symptoms will be measured and assessed every 5 minutes until subject's PG is  $\geq 70$ mg/dL
  - b. Plasma Glucose and assessment of hypoglycemia symptoms will be measured and assessed every 10 minutes until subject's PG is between 90-110 mg/dL or the subject reaches Euglycemia.
2. When PG is  $>70$  mg/dL, the IV glucose infusion is stopped.
3. The subject will be offered a standardized meal. Euglycemia is confirmed in this recovery period.
4. The subject may be discharged when deemed medically stable by the investigator, per CRU criteria.
5. The subject's outpatient insulin dosing will be resumed to their baseline setting, after discharge from the CRU.

#### 9.5. Visit Structure

A schedule of assessments for this study is provided below in [Table 6](#). All visits should occur relative to the randomization which is day zero.

##### 9.5.1. Visit 1 - Screening (Day up to 25 days + 5)

Subjects will be screened to confirm they meet the inclusion/exclusion criteria for the study. Prior to completing any screening activities, the investigator or study team member will obtain informed consent from each subject in accordance with the procedures described in [Section 14.3. Subject Information and Consent](#). Assessment of inclusion/exclusion criteria by a study investigator, including a review of the subject's medical history.

1. Demographic data collection
2. Concomitant medication review
3. Recording of the subject's insulin correction factor (i.e., the reduction in blood glucose in mg/dL per 1 unit of insulin taken).
4. Assessment of vital signs, including measurement of BP, after a 5-minute seated rest.
5. Physical examination, excluding breast, pelvic and genitourinary exams.
  - Measurement of height and weight
6. Performance of a 12-lead ECG (after subject has completed a 10-minute supine rest.)
7. Urine pregnancy test for women of childbearing potential.

8. Rapid Urine drug screen.
9. Collection of venous blood for the following tests as outlined in the Schedule of Activities: hemoglobin A1C, complete blood count (without differential), complete metabolic panel (CMP), screening for HIV, HBV and HCV (Table 8), and immunogenicity testing.
10. The subject will complete the Gold Scale
11. The subject will be asked if he/she has a smartphone for the logging, and if not order a smartphone for subject use during the study.
12. The subject will be instructed to continue their usual diabetes management.
13. Once laboratory results are obtained and a final determination of eligibility is made, subject will be contacted to schedule visit 2 for initiation CGM baseline assessment.  
\*\* If a subject is outside of the screening window, the laboratory assessments will need to be repeated before enrollment.

#### **9.5.2. Visit 2 (Day -7 ) Initiation of Baseline CGM Assessment and Diary Data Collection**

The subject will arrive at the clinic and the following procedures will be completed:

1. Eligibility review
2. Recording of the subject's insulin correction factor (i.e., the reduction in blood glucose in mg/dL per 1 unit of insulin taken).
3. Review Adverse Events
4. The subject will receive and be trained in the use of the glucose meter and strips for use in the study during the CGM data collections periods.
5. The study personnel will assist the subject with downloading the iPRO mylog App and creating the appropriate account to allow synchronization with the CGM data.
  - a. Each site is provided with their specific clinic i.d. from the sponsor
6. The subject will have the blinded iPRO2 CGM device assigned, inserted and initiated according to the manufacturer's instructions. The iPRO2 device ID will be logged for later entry into the eCRF.
7. The importance of using the study glucose meter no less than 12 hours apart will be emphasized for the subject.
  - a. Subjects must perform blood glucose readings at a minimum of twice per twenty-four hour period.
8. The subject's clinical practice glucose, insulin, diary and pump data, if applicable, leading up to the visit will be reviewed and any dose adjustments as required will be made.
  - a. An Insulin Diary will be provided to the subject to collect the following, daily:

- Total daily dose
  - Total Daily Bolus
  - Basal Rate
9. Schedule the subject's next visit and provide the following reminder:
- a. Subject should not administer any long acting insulin dose after dinner the day before the induction procedure.
  - b. Sensors will only hold 7 days of data. Should a subject receive an alert from the iPro app, S/He should contact the site for guidance.

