### **8.1. Inclusion Criteria**

1. Males or females diagnosed with type 1 diabetes mellitus for at least 24 months.
2. Random serum C-peptide concentration < 0.6 ng/ml at Screening.
3. Age 21-64 years, inclusive, at screening.
4. Documented Hypoglycemia unawareness as evidenced by a Gold Scale score  $\geq 4$ , at screening
5. Medical history of an episode of severe hypoglycemia as reported by patient < 50 mg/dL, in the 1 year prior to screening.
6. Current use of multiple daily dosing insulin treatment (< 1 U/(kg\*day) total daily dose) either administered with subcutaneous injections or continuous subcutaneous insulin infusion (CSII).
7. Performs monitoring of glucose minimally 3 times a day. Patients using continuous glucose monitoring for monitoring should continue to do so during the course of the study.
8. Willingness to provide informed consent and follow all study procedures, including using the Medtronic smartphone application "iPRO2mylog" for diabetes data logging and attending all scheduled visits.

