**9.5.9. Visit 8 (Week 12±1 week)**

**CGM Resumption for 3-Month Follow Up**

This visit can occur at any time of day as is least cumbersome for subject and clinic scheduling. The following will occur.

1. Concomitant Medication Review
2. AEs since the last visit will be recorded.
3. The subject's dedicated blood glucose meter and iPRO2 recorder will be retrieved from storage and the subject will resume use as well as the iPRO2mylog diary with the insertion of a new CGM sensor.
4. The subject will be given a supply of BGM strips until the next visit a week later, to verify calibration of the CGM.
5. The Insulin Diary will be given to the subject to collect the following, daily:
  - Total Daily Dose
  - Total Daily Bolus
  - Basal Rate
6. The next visit will be scheduled.

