#### **9.5.11. Visit 10 (Week 25±1 Week)**

##### **CGM Resumption for 6-Month Follow Up**

The visit procedures are identical to those on Visit 8 week 12 as described in section 9.5.8.

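### Protocol 9.5.2 (Visit 2), step 7 is worded as a minimum 12-hour gap between study-meter readings, where step 7a and the meter's purpose call for a maximum gap

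*Protocol*

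**What the plan says.** Visit 2 starts the baseline CGM week. At step 6, "The subject will have the blinded iPRO2 CGM device assigned, inserted and initiated". Step 7 then says: "The importance of using the study glucose meter no less than 12 hours apart will be emphasized for the subject". Directly beneath it, step 7a says: "Subjects must perform blood glucose readings at a minimum of twice per twenty-four hour period".

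The meter's purpose is given in Protocol 8.8, headed "Glucose Meters for Self-Monitoring and Calibration of the CGM Devices". That section requires subjects to use the supplied meter during the CGM collection periods. The calibration role returns at Visit 8: "The subject will be given a supply of BGM strips until the next visit a week later, to verify calibration of the CGM". Visit 10 refers back to Visit 8 ("The visit procedures are identical to those on Visit 8 week 12"). Neither of those visits states a spacing.

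Three other places bear on how often subjects test:
- Section 9.1 has insulin doses reviewed and adjusted during run-in and treatment, to a pre-prandial target of 80-130 mg/dL and a post-prandial target below 180 mg/dL.
- Inclusion criterion 7 describes the enrolled population: "Performs monitoring of glucose minimally 3 times a day".
- Visit 1, step 12: "The subject will be instructed to continue their usual diabetes management".

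**The concern.** A lower bound on the gap between readings is an upper bound on their frequency. Step 7 therefore points the opposite way from step 7a, which sets a lower bound on frequency. Nothing in the protocol gives a reason to keep readings at least 12 hours apart. The meter's stated uses all favor readings that are close enough together.

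The step is an operative instruction that staff are told to stress to the subject. The subjects are selected for a Gold score of 4 or more and a severe hypoglycemic episode in the past year, and they cannot see the study CGM. If one of them took the sentence at face value, it could discourage a further check on the required meter within 12 hours of the last one.

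**Working it through.** **Inputs.** Gap in step 7: 12 h. Floor in step 7a: 2 readings per 24 h. Inclusion criterion 7: at least 3 checks a day. Baseline CGM period: 7 days = 168 h.

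**1. The plan's own figure.** Rate per day = 24 / gap, and 24 / 12 = 2.
- If 12 h is a *maximum* gap, the rate is at least 2 per day, which is the step 7a floor.
- If 12 h is a *minimum* gap, as worded, the rate is at most 2 per day, and at most 168 / 12 = 14 readings in 7 days. The step 7a floor over the same period is 2 × 7 = 14, so the ceiling and the floor coincide.

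**2. Individual schedules.**

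| Gap (h) | Readings per day | Step 7 as worded | Step 7a | Step 7 with *no more than* |
|---|---|---|---|---|
| 6 | 4 | fails | met | met |
| 8 | 3 | fails | met | met |
| 12 | 2 | met | met | met |
| 18 | 1.33 | met | fails | fails |
| 24 | 1 | met | fails | fails |

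Of these schedules, only the 12-hour one satisfies both steps as worded. With the direction changed, step 7 and step 7a agree on every row.

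**3. Slack between step 7 and step 7a as worded.** This depends on how step 7a's 24-hour period is read.
- *Every rolling 24-hour window.* Any two consecutive gaps must sum to at most 24 h. With each gap at least 12 h, both must be exactly 12 h, so the slack is 0.
- *Each calendar day.* Fourteen readings in 7 days have 13 gaps, which need 13 × 12 = 156 h. If the first reading is s hours after midnight on day 1, the last is no earlier than s + 156 h and must fall before 168 h. The slack is 168 − 156 − s = 12 − s hours. The documents give no start time. Assuming 07:00, the last reading is at 19:00 on day 7 at the earliest, leaving 5 h, or 5 / 13 h ≈ 23 minutes per gap. A 06:00 start leaves 6 h and a 09:00 start leaves 3 h.

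**4. Against the rest of the protocol.**
- Pre- and post-prandial readings around one meal fall well within 12 h of each other, so the literal wording would not allow both on the study meter.
- Three checks a day have a mean gap of 24 / 3 = 8 h, whereas three gaps of at least 12 h need 36 h. Over 7 days that is 21 checks against a cap of 14. This support is indirect, because criterion 7 describes a habit at entry and sets no study-meter schedule.

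**The case against.** The best defense is that steps 7 and 7a are delivered together. Step 7a fixes how many readings are required, and step 7 may only ask that those required readings be spread out. No text forbids testing in between. Visit 1, step 12 keeps usual management in place, section 9.1 presupposes meal-related readings, and section 8.7 lets subjects keep their own CGM. Step 6 defers to manufacturer's instructions that are not in the documents, so the intended interval cannot be confirmed.

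Part of this stands. The spreading reading is possible, the two steps can both be met, and the context makes a ban on testing implausible. However, the sentence is not limited to the two required readings, and neither step 7a nor Visit 1, step 12 states a spacing that would correct it. Falling back on another meter is also a weak answer, since section 8.8 requires the supplied one.

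A reader might go further and infer that the baseline CGM data are compromised, or that subjects are forbidden to check symptoms. The documents support neither. They state no calibration interval from which a loss of CGM accuracy could be derived, and nothing links the sentence to the 6-day CGM criterion or to plasma epinephrine. Secondary objective 6 does not show that symptom-prompted readings are required, because item 6b provides for symptomatic events without a meter reading.

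**Conclusion.** The wording is wrong in direction and should be corrected, at minor severity. As written, it turns step 7a's floor of two readings per 24 hours into a ceiling and leaves between no slack and a few hours over a week for meeting both steps. The zero-slack figure assumes rolling windows, and the 5-hour figure assumes calendar days and a 07:00 start. Neither amounts to a strict contradiction.

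The sentence appears only at Visit 2. The practical risk is a discouraged extra check during the baseline CGM week, in a population where such checks matter. Sample size, alpha and the primary analysis are untouched.

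That a maximum gap was intended is an inference from step 7a, section 8.8 and section 9.1. The 12-hour figure is the protocol's own and has not been checked against the device's instructions.

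**What to change.** In Protocol 9.5.2, step 7, replace *no less than* with *no more than*, so that readings are at most 12 hours apart. If the CGM manufacturer's instructions cited in step 6 set a different calibration interval, use that one. Keep step 7a, and add a sentence saying that further readings are unrestricted and are encouraged when symptoms occur. Make the same change in any matching subject instruction.

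Repeating the wording where the meter is resumed at Visits 8 and 10 is optional, since nothing there is wrong. The cost is one phrase and one added sentence, with no new procedures and no change to the analysis.
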